### **8.1.4 Unscheduled Visits**

Subject data obtained during unscheduled visits/assessments will not be summarized, but will be included in subject data listings only.

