 C-SSRS should be conducted at any unscheduled visits.

 To be performed after all baseline assessments.

 Subjects enrolled in Part B only.

 Completed only if participant endorses a positive response to paranoid personality disorder, antisocial personality disorder, and borderline personality disorder on the SPQ.

Visit Number	Screening		Treatment Period												Follow-Up Period					ET
	1	2	3	4	5	6	7	8	9	10	11	12	13	14	15	16	17	18	19	-
Visit Session	Scrn	BL/ Prep	Treatment 1			Treatment 2			Treatment 3			Treatment 4			FU1	FU2	FU3	TC	FU4 /EOS	ET visit
Study Day(s)	-28 to BL	-4 to - 1	1	2	3 (+1)	8 (±1)	9	10 (+1)	15 (±1)	16	17 (+1)	22 (±1)	23	24 (+1)	29 (±1)	36 (±2)	43 (±2)	57 (±2)	64 (±3)	-
AEs			X	X	X	X	X	X	X	X	X	X	X	X	X	X	X	X	X	X
Con Meds	X	X	X	X	X	X	X	X	X	X	X	X	X	X	X	X	X	X	X	X
CAPS-5 (past-week; central rater)		X			X			X			X			X	X	X	X		X	X
MADRS (central rater)		X			X			X			X			X	X	X	X		X	X
CGI-S (central rater)		X			X			X			X			X	X	X	X		X	X
CGI-I (central rater)					X			X			X			X	X	X	X		X	X
PCL-5	X	X			X			X			X			X	X	X	X		X	X
BDI-II		X									X				X		X		X	X
SDS		X			X			X			X			X	X	X	X		X	X
WEMWBS		X									X				X		X		X	X
PGI-S		X			X			X			X			X	X	X	X		X	X
PGI-C					X			X			X			X	X	X	X		X	X
PSQI		X													X				X	X
PTGI		X													X				X	X
BIQ 															X					X
Reflection session															X	X	X			

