### **5.6.5 Management of Cardiovascular Events**

Elevations in blood pressure and heart rate are to be anticipated.

The risk of such elevations will be minimized by the inclusion/exclusion criteria and frequent monitoring of blood pressure and heart rate during each dose session.

Blood pressure and heart rate will be closely monitored with readings recorded at least every 30 minutes during the dose session. The study team will attend to clinical signs and symptoms of potential rare complications of the cardiovascular effects of methylone, such as stroke or acute myocardial infarction, during dose sessions. Any symptoms such as chest pain, shortness of breath, neurological deficit or confusion, or other potential indicators of end organ effects, will prompt additional vital sign measurements, and intervention if appropriate, and the participant will not receive any further doses of IMP and will be followed until resolution.

If a participant experiences ischemic type chest pain, whether or not it is associated with hypertensive crisis, they will be given 0.4 mg of sublingual nitroglycerin every 5 minutes as needed for chest pain pending transport to a hospital, and the Site Investigator will be promptly notified.

Further evaluation and management will be determined by the appropriate trained healthcare providers.

Participants experiencing a cardiovascular event associated with dosing that requires an intervention will not receive further dosing.

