### 7.6 Columbia-Suicide Severity Rating Scale

The C-SSRS will be used to assess suicide potential or tendency as a study entry criterion and monitored throughout the study.

The C-SSRS is a semi-structured interview designed to assess the severity and intensity of suicidal ideation, suicidal behavior and non-suicidal self-injurious behavior over a specified time period. The measurement of suicidal ideation is based on five 'yes' or 'no' questions with accompanying descriptions arranged in order of increasing severity. If the participant answers 'yes' to either questions 1 or 2, the intensity of ideation is assessed in five additional questions related to frequency, duration, controllability, deterrents and reasons for the most severe suicidal ideation. Suicidal behavior is assessed by asking questions categorizing behaviors into actual, aborted and interrupted attempts; preparatory behavior, and non-suicidal self-injurious behavior.

If any item(s) on the C-SSRS are answered ‘yes’, the Investigator must review the participant’s responses in order to (a) at the Screening visit and Baseline/Preparatory session to determine the participant’s study eligibility and potential need for referral to a mental health professional, and (b) during the study evaluate the participant’s need for appropriate medical management such as a referral to a mental health professional, or appropriateness of further study drug administration in consultation with the Medical Monitor and Sponsor.

A significant risk of suicide is defined as a ‘yes’ in answer to:

- (a) questions 4 or 5 on the suicidal ideation section; or,
- (b) any questions on any item in the suicidal behavior section.

This must be reported as an AE or SAE as appropriate and followed up accordingly. Additionally, if a participant responds ‘yes’ to any of the suicidal ideation questions 1 through 3, the Investigator should apply clinical judgement to determine the need for reporting this as an AE or SAE and the need for any appropriate referral.

For any participant who responds ‘yes’ to relevant questions post-study drug administration, they will be handled appropriately.

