Suicidal ideation: A “yes” answer at any time from first administration of study drug to any one of the five suicidal ideation questions (Categories 1-5) on the C-SSRS. Suicidal behavior: A “yes” answer at any time from first administration of study drug to any one of the five suicidal behavior questions (Categories 6-10) on the C-SSRS. Suicidal ideation or behavior: A “yes” answer at any time from first administration of study drug to any one of the ten suicidal ideation and behavior questions (Categories 1-10) on the C-SSRS.

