### 8.4.3 Vital Signs

**Per dosing session:** Baseline is defined as the measurements of pre-initial dose during each dosing session.

**Per participant:** Baseline is defined as the measurements collected at Visit 2. Post-baseline vitals were collected at Visit 15.

Where multiple values are recorded at a time for a participant, the mean of the values will be used in the descriptive statistics.

Descriptive statistics for the measured values and change from baseline will be calculated and plotted for each parameter by treatment and timepoint.

Vital signs (SBP, DBP, HR, respiratory rate and body temperature) will be listed for individual participants.

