### 8.4.6 C-SSRS

The number and percentage of subjects with suicidal ideation (Category 1-5) or suicidal behavior (Category 6-10), and Self-injurious behavior without suicidal intent based on the C-SSRS after first administration of study drug will be summarized.

Two shift tables will demonstrate changes in C-SSRS, most severe suicidal ideation (0 to 5), and C-SSRS categories (No suicidal ideation or behavior, suicidal ideation, suicidal behavior) from baseline to post-treatment.

C-SSRS results will be listed for individual participants.

[REDACTED]

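### SAP 8.1.4 sends all unscheduled data to listings, which contradicts the any-time C-SSRS definition in SAP 6.2.6 and 8.4.6 and leaves symptom-prompted readings out of the safety summaries

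*SAP*

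**What the plan says.** The general rule is SAP 8.1.4: "Subject data obtained during unscheduled visits/assessments will not be summarized, but will be included in subject data listings only". It covers visits and single assessments, efficacy and safety alike. The section just before it, SAP 8.1.3 on baseline, allows endpoint-specific exceptions; 8.1.4 does not.

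The protocol generates unscheduled safety data by design:
- Protocol 1.3, footnote 9: "C-SSRS should be conducted at any unscheduled visits".
- Protocol 5.6.5: chest pain, shortness of breath, neurological deficit, confusion and similar signs "will prompt additional vital sign measurements, and intervention if appropriate".
- Protocol 7.1 and SAP 6.2.5: an abnormal laboratory value may lead to further testing.

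The endpoint-specific C-SSRS text points the other way from 8.1.4. SAP 6.2.6 defines suicidal ideation as a yes "answer at any time from first administration of study drug to any one of the five suicidal ideation questions", and defines behavior in parallel over categories 6 to 10. SAP 8.4.6 says that the number and percentage of subjects with ideation, behavior or non-suicidal self-injury "based on the C-SSRS after first administration of study drug will be summarized", and adds two shift tables.

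**The concern.** An unscheduled contact is often made because something has gone wrong. A rule that keeps all such data out of every summary therefore acts on observations that are more likely than average to be abnormal.

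For the C-SSRS the problem is sharper, because the SAP gives two incompatible instructions. A programmer who applies 8.1.4 and one who applies 6.2.6 could produce different suicidality tables from the same data, and nothing in the SAP settles which is right. Suicidality is a key safety outcome in this population: Protocol 4.4 names it as a reason for having the placebo control. The table should not depend on which section the programmer read last.

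**Working it through.** No stated figure is in dispute. The check sets the texts side by side and then sizes the effect on one table.

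**1. C-SSRS texts compared**

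| Source | Which assessments count |
|---|---|
| SAP 6.2.6 | Any yes at any time from first administration |
| SAP 8.4.6 | C-SSRS after first administration, summarized |
| SAP 8.1.4 | Scheduled only; unscheduled data go to listings |
| Protocol 1.3, footnote 9 | C-SSRS is performed at unscheduled visits |

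The four cannot all be followed once one participant has a positive response only at an unscheduled contact.

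**2. How much the scheduled contacts already cover**

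The Schedule of Assessments has 16 scheduled C-SSRS contacts after the Day 1 dose (Visits 4 to 19). Nominal gaps are at most 5 days up to Day 29, then 7, 7, 14 and 7 days to Day 64. The longest, 57 − 43 = 14 days, falls late in follow-up.

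**3. What the adverse-event route recovers**

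- Ideation items 4 or 5, or any item of the suicidal behavior section: Protocol 7.6 says "This must be reported as an AE or SAE as appropriate and followed up accordingly". Protocol 7.8.1.1 collects AEs at all interactions, and SAP 8.4.1 tabulates TEAEs and AESIs. These are recovered if they are TEAEs.
- Ideation items 1 to 3: under Protocol 7.6 they become an AE only by investigator judgement. They are not reliably recovered.
- Late events: SAP 8.4.1 ends the TEAE window 7 days after the last dose unless a relation to drug is suspected. With the last dose on nominal Day 22, that is 22 + 7 = Day 29. An unrelated event starting between Day 30 and Day 64 is not a TEAE.

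**4. Size in the C-SSRS incidence table**

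SAP section 4 plans 32 per arm. One omitted participant is 1/32 = 3.1 percentage points. The documents give no rate of positive responses seen only at unscheduled contacts, so the rows below rest on assumed counts in one arm.

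| True cases | Seen only at unscheduled contacts | True incidence | Incidence shown under 8.1.4 |
|---|---|---|---|
| 2 | 0 | 2/32 = 6.25% | 6.25% |
| 2 | 1 | 6.25% | 1/32 = 3.1% |
| 2 | 2 | 6.25% | 0% |
| 4 | 1 | 4/32 = 12.5% | 3/32 = 9.4% |
| 4 | 2 | 12.5% | 2/32 = 6.25% |

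**5. Vital signs and laboratory tests**

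- Scheduled BP and HR are dense: 480 min / 30 min = 16 post-dose times in an 8-hour session, 4 × 16 = 64 over four sessions. SAP 8.4.3 summarizes them by treatment and timepoint.
- A symptom-prompted reading between those times is unscheduled and goes to listings. It reaches a table only through an AE. The hypertension AESI (SAP 6.2.1.3) requires SBP ≥160 or DBP ≥100 mmHg together with more than one drug or intensified therapy, so a high reading alone does not qualify.
- Routine laboratory draws after first dosing are Day 15 and Day 29 only (plus early termination before Day 29). A repeat liver test between or after them would be outside the descriptive and shift tables of SAP 8.4.2.
- The visible SAP text describes no worst-value or threshold table in which such readings would appear.

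**The case against.** The strongest reply is that the serious events are caught elsewhere. Items 4 and 5 and suicidal behavior are mandatory AEs or SAEs, AEs are collected at every interaction, and suicide-risk events, significant cardiovascular events and treated Grade 3 hypertension are AESIs with their own line in the overall TEAE summary. Protocol 9.5.1.1 also speaks of summarizing all AEs and SAEs, although SAP 8.4.1 narrows the tables to TEAEs. Nothing is lost from the listings. This stands. A reader might infer from 8.1.4 that crisis-visit suicidality disappears from the safety tables altogether, and the documents do not support that. What remains is the residue in step 3.

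Second, the specific text of 6.2.6 and 8.4.6 can be said to override a general rule. That is a sensible reading, but the SAP does not state it, so the exclusion is an unresolved contradiction and not a settled outcome.

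Third, keeping off-schedule readings out of by-timepoint means is ordinary practice, and including them would distort those means. This also stands: the planned by-timepoint vital-sign summaries are not at fault. SAP 8.4.3 adds: "Where multiple values are recorded at a time for a participant, the mean of the values will be used in the descriptive statistics". That averages only values recorded at the same time, and a later prompted repeat need not fall under it. Continuous summaries also show the maximum at each timepoint.

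Fourth, table shells are in a separate file and text after SAP 8.4.6 is redacted, so the absence of a worst-value table can be asserted only for the visible text.

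**Conclusion.** The contradiction between SAP 8.1.4 and SAP 6.2.6/8.4.6 is real and should be resolved before database lock. Read literally, 8.1.4 gives C-SSRS incidence and shift tables that do not match the SAP's own definition, by 3.1 percentage points for each participant whose only positive response came at an unscheduled contact. The responses most exposed are ideation items 1 to 3 not judged to be AEs, and unrelated events after about Day 29. Symptom-prompted vital signs and follow-up laboratory values are a secondary gap of the same kind.

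A reader might go further and conclude that methylone's acute risk is understated, or that the safety comparison is biased toward no difference. The documents do not show this. The rule applies to both arms, no rate of unscheduled-only events is given, and the in-session profile is measured every 30 minutes on schedule. Protocol 5.6.3 describes suicidality as a recognized complication of PTSD and not an anticipated treatment effect, so unscheduled contacts for it could be as frequent on placebo. Omission can only lower the count within an arm; the direction and size of any difference between arms are unknown.

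**What to change.** 1. Limit SAP 8.1.4 to by-visit efficacy summaries and by-timepoint descriptive summaries.
2. State in SAP 8.4.6 that the C-SSRS incidence tables, and shift tables from baseline to the worst post-baseline value, use every assessment after first administration, scheduled or unscheduled.
3. As a small addition, give one descriptive table by arm of worst post-dose SBP, DBP, HR, temperature and liver tests, including unscheduled and unaveraged values. Count participants at the numerical limits that Protocol 4.8 already states: SBP ≥160 or DBP ≥100 mmHg; temperature rise >2.0 °C and ≥38 °C; AST or ALT >5 × ULN, or >3 × ULN with the accompanying bilirubin condition. Protocol 4.8 gives no heart-rate limit, so HR would be shown as the worst value only.

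The cost is a few sentences in the SAP and one extra descriptive table. No new data are collected and no dosing or stopping rule changes.

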### **8.1.5 Multiplicity**

Findings from this study will be used to design and power future clinical trials to further evaluate the efficacy and safety of methylene for the treatment of PTSD.

As this trial is not a confirmatory study, multiplicity is not applicable.

### **8.1.6 Tests**

All tests will be based on one-sided significant level of 0.05. In addition to the tests, two-sided 90% confidence intervals will be reported.

### **8.1.7 Covariates**

For the analysis of select efficacy endpoints, the baseline value will be included (if applicable) as a covariate. Sex will also be used as a covariate.

## **8.2 Subject Information**

### **8.2.1 Subject Disposition**

Subject disposition will be tabulated with the following numbers (%) of subjects: total screened, screen failure (along with screen failure primary reason), randomized, study drug treated, completed study drug (early discontinued from study drug, along with primary reasons), completed study (discontinued from study, along with primary reasons).

The number of subjects in each analysis populations (mITT Population, Per-protocol Population, and Safety Population) will be reported.

Data listings will include subject disposition and subjects included in each analysis population.

## **8.2.2 Protocol Deviations**

Important protocol deviations will be classified and documented before analysis and will be summarized in terms of frequency and percentage by category.

All protocol deviations will be presented in a data listing.

## **8.2.3 Demographic and Baseline Characteristics**

### **8.2.3.1 Demographic Data**

Age, sex, race, ethnicity, height, weight, body mass index (BMI), and childbearing potential will be summarized and listed.

### **8.2.3.2 Baseline Characteristics**

Summary of duration of PTSD symptoms (in years, from CAPS-5 conducted at screening), age at end date of index trauma, time since end date of index trauma (years = (ICF date-end date of index trauma+1)/365.25), type of traumatic event (PT MedDRA coding of index event), prior PTSD treatment type, prior psychedelics used, and dissociative PTSD symptoms (Yes = Item 29 or 30 have a severity  $\geq 2$ ) will be summarized.

Lifetime C-SSRS (Lifetime accounts for all suicidal ideation and behavior prior to the study): positive lifetime suicidal ideation (ideation score  $>0$ ), serious lifetime suicidal ideation (ideation score of 4 or 5), positive lifetime suicidal behavior (behavior score  $>0$ ) will be summarized. The same summary for past 2 months suicidal ideation and past 5 years suicidal behavior will be presented.

Data listings will include the information of PTSD duration and other baseline characteristics.

### **8.2.3.3 Medical History**

Medical history will be coded by MedDRA (Medical Dictionary for Regulatory Activities, version 25.1 or higher). Medical history will be summarized according to Preferred Term (PT).

Data listings will include the medical history of subjects.

## **8.2.4 Prior and Concomitant Medication and Procedures/Therapies**

Medications will be coded by WHO Drug Dictionary (version Sep 2022 or higher). Medication is summarized by incidence rate according to Anatomical Therapeutic Chemical 4 (ATC4) and Preferred Name. Procedures/therapies will be coded by MedDRA (version 25.1 or higher), and summarized by incidence rate according to PT.

Prior medication/procedure is any medication that started and stopped before initial dosing of study drug. Concomitant medication/procedure is any medication/procedure received at or after the dose of study drug, medication/procedure that was received before initial dosing and continued after initial dosing of study drug, or medication/procedure with a missing stop date. If a medication/procedure has a missing or partial missing start/end date and it cannot be determined whether it was taken before initial dosing or concomitantly, it will be considered as concomitant.

Prior and concomitant medication and procedures will be listed separately.

## **8.2.5 Treatment Exposure and Compliance**

The number of doses administered by dosing session will be summarized.

Drug administration information will be listed by subject.

## 8.3 Efficacy Analysis

These analyses will be based on the mITT Population. All efficacy endpoint data will be listed for individual participants.

### 8.3.1 Statistical Methods

#### 8.3.1.1 Analyses for Continuous Efficacy End Points

A Mixed Model for Repeated Measures (MMRM) will be fitted for select efficacy endpoints to analyze the difference between treatments. The model will include treatment, visit, and treatment by visit interaction as fixed effects, where visit is the repeated effect. The endpoints baseline value (if applicable) and sex will be included as covariates.

The covariance structure will be modeled using an “unstructured” (UN). Other covariance structures may be considered if the UN model does not converge, such as AR(1), and CS. The visit-by-treatment interaction allows for potential differences in the treatment effect at different time points. Pairwise contrasts will be constructed to compare the methylene group to the placebo group at each visit specifically.

Besides, summary statistics will be provided for the actual values and for the change from baseline.

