### 9.5.2 **Efficacy Statistical Analysis**

The primary efficacy endpoint is the CAPS-5 total score change from baseline to Week 10 as compared to placebo.

All efficacy endpoint data will be listed for individual participants. All continuous efficacy endpoints will also be summarized by descriptive statistics (n, arithmetic mean, SD, median, minimum and maximum) by study part, overall, by treatment (for Part B) and study period. All categorical efficacy endpoints will be summarized by descriptive statistics (n, percentage).

For Part A the change from baseline to each timepoint will be presented along with a paired *t*-test p-value.

A Mixed Model for Repeated Measures (MMRM) will be fitted for select efficacy endpoints to analyze the difference between treatments for Part B. The model will include treatment, visit, and treatment by visit interaction as fixed effects, where visit is the repeated effect. The baseline value will be included (if applicable) as a covariate. All tests will be based on two-sided significant level of 0.05. Full details of the statistical analysis for each endpoint will be described in the SAP.

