## 4 SAMPLE SIZE DETERMINATION

Sample size calculations for Part B were performed using PASS 2022 to determine the sample size required to detect a significant difference between CAPS-5 scores in the methylone and placebo groups (the efficacy endpoint). A previous phase 3 trial investigating the effects of MDMA versus placebo on CAPS-5 scores found a placebo-corrected treatment effect at the end of treatment of 11 points and a pooled standard deviation (SD) of 12 (Mitchell 2021). Assuming a treatment effect of 11 points and a pooled SD of 12 in this trial, with a sample size of 20 or 27 evaluable participants in each treatment group, the trial should provide 80% or 90% power, respectively. Assuming a dropout rate of 15%, a target sample size of 46 (23 per treatment group) or 64 (32 per treatment group) will provide 80% or 90% power, respectively.

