## 11.3 Appendix 3 MMRM and CMH SAS Sample Code

This MMRM approach can be implemented in SAS by a code similar to the following:

```
proc mixed data = adef method=REML;
  class Subjid trtpn avisitn;
  model Chg=trtpn avisitn trtpn*avisitn base sex/ddfm=kr; /* The baseline value will be
  included (if applicable) as a covariate.*/
  repeated avisitn/ subject = Subjid type=un;
  lsmeans trtpn trtpn*avisitn/diff cl;
  ods output Tests3=b1 LSMMeans=b2 Diffs=b3;
run;
```

This CMH approach can be implemented in SAS by a code similar to the following:

```
Proc freq data=adef;
  Tables trtpn*outcome/cmh riskdiff;
  Weight count;
Run;
```

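### Low severity: the CAPS-5 MMRM fits one baseline slope for all eight post-baseline visits; a prespecified baseline-by-visit term would cheaply protect the precision of the Week 10 contrast.

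*SAP*

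**What the plan says.** SAP 8.3.1.1 gives the mean model: "The model will include treatment, visit, and treatment by visit interaction as fixed effects, where visit is the repeated effect". It then adds: "The endpoints baseline value (if applicable) and sex will be included as covariates". The sample code in SAP 11.3 (Appendix 3) agrees: "model Chg=trtpn avisitn trtpn*avisitn base sex/ddfm=kr". Neither has a product of baseline and visit. The covariance is unstructured, with AR(1) or compound symmetry as possible fallbacks if it does not converge.

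The past-week CAPS-5 row of the Schedule of Assessments (Protocol 1.3) has eight scheduled post-baseline marks: Days 3, 10, 17, 24, 29, 36, 43 and 64. The primary timepoint comes from Protocol 9.5.2: "The primary efficacy endpoint is the CAPS-5 total score change from baseline to Week 10 as compared to placebo". SAP 8.3.2.1 names no visit. Protocol 9.5.2 specifies the same model without sex, and neither document explains the single baseline coefficient.

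**The concern.** The model lets the treatment effect vary freely by visit and leaves the covariance unstructured, yet holds the baseline slope constant over time. A common slope is a weighted average of the visit-specific slopes. If these differ, the Week 10 contrast is adjusted with the wrong coefficient for Week 10, and any chance baseline imbalance between arms is corrected too little or too much.

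Unequal slopes are plausible here. At Day 3, two days after the first dose, the past-week recall window still covers mostly pre-dose days; at Day 64 it does not. Protocol 2.4.1 reports Part A mean changes of −8.4 at Day 3 and −36.2 at Week 10 from a baseline mean of 47.8. If change were proportional to baseline, the slopes would be −8.4/47.8 = −0.18 and −36.2/47.8 = −0.76.

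What is at stake is the precision of the primary contrast and, under one further condition, how the model carries missing Week 10 scores, because SAP 7.1 analyses available data without imputation.

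**Working it through.** **The plan's own figure.** SAP 4 states: "Assuming a treatment effect of 11 points and a pooled SD of 12 in this trial", and "with a sample size of 20 or 27 evaluable participants in each treatment group, the trial should provide 80% or 90% power, respectively". With 27 per arm the noncentrality is 11/(12 × √(2/27)) = 11/3.266 = 3.37 on 52 degrees of freedom. Power is 91.1% at two-sided 0.05 (Protocol 9.2); 26 per arm gives 89.99%. Then 27/0.85 = 31.8, so 32 per arm and 64 in all. The stated figure reproduces. At the one-sided 0.05 of SAP 8.1.6, 27 per arm gives 95.3%. The calculation takes no credit for baseline adjustment.

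**Formula.** Let β_v be the baseline slope at visit v, Σ the residual covariance across visits, s_B the baseline SD and σ₁₀ the Week 10 residual SD.
- Common slope in large samples: b* = Σ w_v β_v, with weights w = Σ⁻¹1 / (1′Σ⁻¹1).
- Week 10 residual variance with visit-specific slopes: σ₁₀².
- Week 10 residual variance with a common slope: σ₁₀² + (β₁₀ − b*)² s_B².
- With complete data, the SE ratio (common over visit-specific) is the square root of the ratio of these variances.

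**Assumptions, none given in the documents.** Total SD of Week 10 change 12; correlation 0.9 per visit step; s_B 6, 8 or 10; Day 3 slope −0.1 or −0.2; Week 10 slope −0.4, −0.6 or −0.8; Day 3 change SD 6, 9 or 12. Slopes and SDs move linearly in log study day from Day 3 to Day 64.

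**One case in full** (s_B 8, slopes −0.2 to −0.6, Day 3 SD 9):
- σ₁₀² = 144 − 0.6² × 64 = 120.96, SD 11.00.
- b* = −0.302, so the added variance is 0.298² × 64 = 5.68; total 126.64, SD 11.25.
- SE ratio √(126.64/120.96) = 1.023. Power at 27 per arm is 94.1% against 95.0%.
- In participants: 64 × (1 − 120.96/126.64) = 2.9, or about 3 of 64 in this case.

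**Range of SE ratios** over s_B 6–10 and Day 3 slope −0.1 or −0.2:

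| Week 10 slope | Day 3 SD 12 | Day 3 SD 9 | Day 3 SD 6 |
|---|---|---|---|
| −0.4 | 1.00–1.01 | 1.00–1.02 | 1.01–1.05 |
| −0.6 | 1.00–1.01 | 1.01–1.05 | 1.03–1.14 |
| −0.8 | 1.01 | 1.03–1.08 | 1.07–1.28 |

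Across the grid the common-slope Week 10 residual SD was 9.0 to 12.0. The weight on the first four visits was 77–89% at Day 3 SD 6 but 30–49% at Day 3 SD 12, where Day 64 alone carried 40–80%.

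**Simulation** (64 randomised, 15% monotone dropout unrelated to baseline, unstructured covariance, 1,000 runs per row, sex omitted, approximate REML):

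| s_B | Slopes | Day 3 SD | Empirical SE ratio |
|---|---|---|---|
| 8 | −0.4, equal | 9 | 0.995 |
| 8 | −0.2 to −0.4 | 9 | 1.004 |
| 8 | −0.2 to −0.6 | 12 | 1.009 |
| 8 | −0.2 to −0.6 | 9 | 1.023 |
| 8 | −0.2 to −0.6 | 6 | 1.046 |
| 10 | −0.2 to −0.8 | 6 | 1.197 |

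The mean estimate was −11.0 under both models in every row. In the equal-slopes row the interaction costs 1/0.995 − 1 = 0.5% in empirical SE; the ratio of mean model SEs, 0.992, gives 0.8%.

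**Baseline-dependent dropout** (large samples, slopes −0.2 to −0.6, about 14% dropout, true effect 11). Same relation in both arms: the models differ by 0.03 points. Relation in one arm only: about 0.2. Opposite directions by arm: about 0.5, with the interaction model nearly unbiased. A second check with about 15% dropout gave no difference when the arms were alike and roughly 0.3–0.55 when they were not.

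**Fallback covariances** (complete data, constant variance). Under compound symmetry all visits weigh equally, so Week 10 gets 1/8. Under AR(1) with correlation 0.9 it gets 1/(2 + 6 × 0.1) = 38%.

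**The case against.** The strongest reply is that nothing here is an error. Protocol and SAP agree on baseline as a covariate, the model is prespecified, randomisation protects the treatment estimate, and SAP 8.1.5 calls the trial non-confirmatory. The sample size rests on SD 12 without adjustment, and the common-slope model did no worse than that. All of this stands, and it keeps the severity low.

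The reply also rightly stops four stronger readings that a reader might infer.
- That the slope is set largely by early visits. Under an unstructured covariance the weights depend on visit variances and correlations that the documents do not give; with equal SDs, Day 64 can carry most of the weight.
- That Part A proves the slopes differ. Its mean changes are compatible with identical slopes at every visit. It had 14 treated participants and no placebo arm, whereas the Part B slope is pooled over both arms.
- That the extra term is free. An unstructured 8 × 8 covariance already has 36 parameters, for about 54 to 64 participants, and the term costs a little precision if the slopes are equal.
- That dropout related to baseline severity is enough to distort the estimate. It is not, if the relation is the same in both arms.

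These limits narrow the point but do not remove it. The term is standard, its cost is under 1% in SE in the equal-slopes simulation, and holding this one coefficient constant has no stated reason.

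**Conclusion.** The point holds as a cheap improvement of low severity. The Week 10 contrast is adjusted with a slope set partly by other visits. If the true slopes differ, the common-slope model gives up roughly 0–5% of Week 10 SE for slopes drifting from −0.1 or −0.2 to −0.4 or −0.6 with baseline SD 6–10, provided Day 3 SD is at least about three quarters of the Week 10 SD. The loss grows with steeper drift and more sharply rising variance, and is largest (up to 28% in the grid) when these meet wide baseline spread. If the slopes are equal, nothing is lost.

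The documents give no baseline SD, visit slopes or visit correlations, so they cannot settle where in this range the trial lies. They support neither a claim of bias with complete data nor a claim that the planned power is missed. The missing-data difference, about 0.2 to 0.5 of 11 points, needs a relation between baseline and dropout that differs by arm.

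**What to change.** Before unblinding:
- In SAP 8.3.1.1, add baseline-by-visit interaction to the fixed effects of the primary CAPS-5 MMRM.
- In SAP Appendix 3, add `base*avisitn` to the MODEL statement.
- Apply the same term to the other MMRM endpoints for consistency; the calculations above concern CAPS-5 only.
- If the extra parameters are a worry, keep the common-slope model as a named sensitivity analysis.

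The cost is one parameter per post-baseline visit beyond the first: 7 for CAPS-5 and the other scales on the eight-visit schedule, 3 for BDI-II and WEMWBS (four visits), and 1 for PSQI (two visits). For CAPS-5, the SE rises by about 0.5–0.8% if the slopes are in fact equal. No data collection changes. The timing matters because choosing the term after seeing unblinded results would be data-driven.
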